Delirium occurrence rates for hospitalized older adults range from 29-64%. Although 30-50% of delirium is preventable, it frequently goes unrecognized until acute and potentially devastating. The Hospital Elder Life Program (HELP) is a multidimensional clinical strategy that is effective in preventing delirium, but labor intensive. This randomized controlled study will test an innovative method to implement the HELP approach: a tablet-based digital avatar that can see, hear, and talk with a patient using speech-to-text technology. The avatar platform has already been validated at Jamaica Hospital in a previous study in 2016: “GeriJoy: The Use of an Avatar Virtual Service Animal to Improve Outcomes in Hospitalized Older Adults” as well as in multiple published studies to effectively provide psychosocial support to older adults across varied clinical settings. This study will focus on discerning the relative impact of implementing HELP through this technology. Participants aged 65+ will be randomly assigned to receive one of the following interventions in addition to usual care throughout their hospitalization: 1) an avatar delivering HELP protocols and socialization; or 2) no intervention beyond usual care. Participants will be assessed by the investigators upon admission to the study and reassessed upon 24-hour discharge notification using the Short Portable Mental Status Questionnaire (SPMSQ), Memorial Delirium Assessment Scale, and Short CAM (Confusion Assessment Method). Based on patient medical records of sedation, restraints and incidence of falls and delirium, pre- and post-assessment scores will be compared using paired t-tests to determine outcomes among the groups. If the avatar is effective in improving outcomes by providing HELP interventions, the number of patients who benefit from HELP could increase greatly due to technology-enabled cost efficiencies, and protocol and data collection standardization across many sites.

Specific aims/hypotheses

For hospitalized older adults, will the use of an avatar delivering HELP protocols...

1. decrease delirium incidence and severity,
2. decrease falls and falls with injury,

..more than usual care?

Background and significance

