Study design: This randomized controlled trial will compare outcomes on delirium, falls, sitter utilization (1:1's) and restraints between the two study groups: HELP-protocolized avatars, and usual care. Each day of the study, enrollment of subjects will proceed with randomization of each subject between groups (the randomization primarily effects delirium data, which is assessed by subject) until there are no more available intervention devices. However, falls and other unit-level grouping are non-randomized (see below).

Sample Size: A total of 3,650 patients (avatar and usual care) are expected to be enrolled at JHMC over the course of two years, based on an estimated average length of stay of 4 days.

Study Units: Patients will be recruited from the following units at JHMC: 3S, 3N, 4S, IMCU, 5N, 6S, and Hospice. Because the hospital only collects/reports unit-by-unit quarterly falls data, we will take the following measures to ensure that falls data collected for study purposes are a valid indicator of possible intervention effect:

- There are expected to be protocol and technical adaptations made during the first quarter of the study, and the study will not begin enrolling subjects exactly at the start of a calendar quarter. Therefore, the first calendar quarter of falls data is not intended to provide useful data regarding unit-level falls outcomes, and enrollment of patients may be performed on select units by convenience.
- Starting on the first day of the first full calendar quarter, a unit-equitable enrollment protocol will be implemented in which one or more of the study units at any time may be formally designated for active subject enrollment, and such designated study units will have their enrollment numbers monitored and rounding adjusted as needed to ensure that, on average, each designated unit receives a similar number of intervention patients at any time. Which units are designated or not designated for enrollment may be changed at the start of each calendar quarter to compare the effect of the intervention and to control for annual changes in fall rates. Research assistants will not enroll any patients on units not designated for enrollment, but will continue to round currently enrolled patients until they are dis-enrolled.

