Sample inclusion and exclusion criteria: All patients over age 65 on the pilot units who can provide informed consent or who have a proxy who can provide informed consent will be assessed by the investigators. Those who consent will be randomly assigned to one of the two treatment conditions unless they meet any of the exclusion criteria: a.) aggression or combativeness with intent to harm self or others, b.) alcohol or drug withdrawal, c.) severe hearing impairment and simultaneous severe vision impairment, despite assistive devices, d.) cannot verbalize fluently in either Spanish or English, e). on 1:1;if a study subject is put on 1:1 during the duration of the study, he/she will be unenrolled from the study, f) expected to be discharged within the next 24 hours.

Instruments

Pre- and post-intervention:

1. Short Portable Mental Status Questionnaire
2. Short CAM (Confusion Assessment Method) – also conducted during each daily round
3. Memorial Delirium Assessment Scale – if CAM screens positive

Statistical analyses: Demographic variables including age, gender, education, race/ethnicity, and living arrangements will be collected to determine equivalency of study groups. Pre-and post-assessment scores will be compared using paired t-tests to compare means at baseline and at hospital discharge within each group, and between groups. All data will be analyzed using the Statistical Package for Social Sciences software (SPSS, Inc. Chicago, IL). Statistical significance will be defined as $p \leq 0.05$.

Additional Information

Photos of Avatar

Figure D.8.1: A hospitalized older adult in South Carolina enjoys the company of an avatar as it plays music and shows a photo. A “fisheye lens” mounted to the top of the avatar device enables wide-angle visual monitoring, to enable appropriate reaction by the avatar to not only the patient’s facial and body language cues, but also any dangerous unassisted transfers, tugging on IV lines, etc. To help with re-orientation, the window behind the avatar reflects the actual weather report, and the lighting of the avatar’s environment reflects day or night status. A video showing the patient talking to the avatar and singing along is available at <https://www.youtube.com/watch?v=WfWjazOmKUk>

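### The plan names no covariate-adjusted comparison between groups, so it gives up precision that the baseline SPMSQ could supply at almost no cost

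*Combined protocol and SAP*

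**What the plan says.** The Statistical analyses section of the combined protocol and SAP lists age, gender, education, race/ethnicity and living arrangements, and says that these variables "will be collected to determine equivalency of study groups". It gives no test, margin or consequence for that step. Scores are to be "compared using paired t-tests to compare means at baseline and at hospital discharge within each group, and between groups", with significance set at 0.05. No regression, ANCOVA, stratified analysis or covariate is named anywhere in the document.

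The baseline scores themselves are collected. The opening summary has patients "assessed by the investigators upon admission to the study and reassessed upon 24-hour discharge notification". The Instruments section lists the "Short Portable Mental Status Questionnaire" and the Short CAM before and after the intervention, and the "Memorial Delirium Assessment Scale – if CAM screens positive".

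The Study design section says that randomisation bears mainly on the delirium data, which are assessed by subject. Falls and other unit-level groupings are stated to be non-randomised.

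**The concern.** Two things are at stake in the individually randomised comparison.

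The first is precision. The baseline SPMSQ is planned for every patient, and age and unit are known at enrolment. All three plausibly predict cognition at discharge. The seven study units include IMCU and Hospice, and the units open to enrolment may change each quarter, so unit is a reasonable candidate. None of these enters as a covariate, so the standard error of the between-group difference is likely to be larger than the collected data require.

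The second is an unplanned choice of analysis. In this comparison, differences between the groups at randomisation arise by chance, and a non-significant difference would not show that the groups are equivalent. A check with no stated consequence leaves room to decide on adjustment after the data are seen.

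**Working it through.** **The plan's own figure.** The Sample Size paragraph says: "A total of 3,650 patients (avatar and usual care) are expected to be enrolled at JHMC over the course of two years". It rests on a mean stay of 4 days. Over 730 days, 3,650 × 4 / 730 = 20 patients enrolled at any time. The documents do not state that number, nor any SD, effect size, power or allocation ratio. The 3,650 is therefore a capacity figure, and there is no power calculation to reproduce.

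**Change score against ANCOVA.** Assumptions: the between-group analysis compares change scores; pre and post variances are equal (σ²); the pre-post correlation r is the same in both arms. The variance per patient is then:

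- change score: 2σ²(1 − r)
- ANCOVA on baseline: σ²(1 − r²)
- ratio of ANCOVA to change score: (1 − r²) / [2(1 − r)] = (1 + r)/2

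The documents give no r, so a range is shown.

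| r (assumed) | Change score (σ² = 1) | ANCOVA (σ² = 1) | Ratio | Change-score patients needed per ANCOVA patient |
|---|---|---|---|---|
| 0.3 | 1.40 | 0.91 | 0.65 | 1/0.65 = 1.54 |
| 0.5 | 1.00 | 0.75 | 0.75 | 1/0.75 = 1.33 |
| 0.7 | 0.60 | 0.51 | 0.85 | 1/0.85 = 1.18 |
| 0.9 | 0.20 | 0.19 | 0.95 | 1/0.95 = 1.05 |

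**Absolute scale.** Assume all 3,650 patients are analysed 1:1 (1,825 per arm), two-sided 0.05 and 80% power. The detectable difference, in SDs of the raw score, is (1.96 + 0.84) × √(2/1,825) × √(variance per patient), that is, about 0.0927 × √(variance per patient).

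- r = 0.5: 0.093 (change score) against 0.0927 × √0.75 = 0.080 (ANCOVA)
- r = 0.7: 0.0927 × √0.60 = 0.072 against 0.0927 × √0.51 = 0.066

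**Demographics alone.** Linear adjustment multiplies the standard error by √(1 − R²). R² is assumed. At 0.02 the factor is 0.990 (1.0% smaller); at 0.05 it is 0.975 (2.5% smaller). Nearly all of the gain therefore comes from the baseline score.

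**Equivalency check, if done by significance tests.** With five independent tests at 0.05, 1 − 0.95⁵ = 0.226, so about 23% of correctly randomised trials would flag at least one variable. The figure changes if the variables are correlated or if more than five are tested.

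**The case against.** The strongest case against is that this is a preference about efficiency in a large trial. Change-score and ANCOVA comparisons are both unbiased under randomisation. With 3,650 patients, detectable differences are below 0.1 SD either way at r = 0.5 or 0.7, and at r = 0.9 the gain is only 5%. Delirium is the first aim, and the variance formula does not carry over to a binary outcome. All of that stands. It limits the size of the point but does not remove it, because the data are already to be collected.

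Four stronger readings are tempting, and the documents do not support them:

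- *That the plan tests baseline differences for significance.* It names no test for that step, and a descriptive table fits the wording. The 23% is conditional.
- *That baseline information is ignored.* That is true only of the demographics. Baseline scores enter the pre-post comparison, though not as covariates.
- *That randomisation guarantees balance, so comparability never matters.* It balances in expectation, and only for the individually randomised data. Falls are non-randomised. Patients placed on 1:1 observation are unenrolled after randomisation, so the analysed groups could differ for reasons other than chance.
- *That ANCOVA should be credited with its gain over an analysis of discharge scores alone.* The plan describes no such analysis, so that is not the right comparator.

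The change-score comparator is itself an inference. A paired t-test does not compare two independent arms, so the between-group method is not properly defined. That strengthens the case for stating a model.

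**Conclusion.** The point holds as a recommended improvement in efficiency and pre-specification. It is not evidence of bias in the randomised comparison. For the SPMSQ, ANCOVA on the baseline score would cut variance relative to change scores by 35%, 25%, 15% and 5% at r = 0.3, 0.5, 0.7 and 0.9. The direction holds for any r below 1 with equal pre and post variances; the size depends on an r that the documents do not give. Demographics alone would contribute about 1–2.5% off the standard error at an assumed R² of 0.02–0.05. No gain is quantified for incident delirium. Adjustment would not by itself repair post-randomisation removals.

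**What to change.** In the Statistical analyses section:

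1. **SPMSQ.** Replace the between-group t-test with a pre-specified ANCOVA of the discharge score on arm, baseline SPMSQ, age and study unit.
2. **Incident delirium.** Among patients CAM-negative at baseline, pre-specify a logistic model on arm, baseline SPMSQ, age and unit, reported as a marginal risk difference, and state how that difference and its standard error are obtained. Baseline MDAS is not a usable covariate here, because it is measured only after a positive CAM.
3. **Baseline characteristics, randomised comparison.** Present them descriptively by arm, and state that no equivalency check will decide which covariates are used.
4. **Falls.** Keep the comparability assessment for the non-randomised, unit-level comparison, and say there that its purpose is to address confounding.

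The cost is a few sentences of plan wording. The covariates are already to be collected or known at enrolment, and SPSS, the named software, fits both models. The marginal risk difference takes one further step from the fitted probabilities.

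### Two aims covering four outcomes, plus sitter use, restraints and possibly sedation, share one unadjusted p ≤ 0.05 with no primary endpoint; with no true effect, at least one significant result has roughly a 13–30% chance

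*Combined protocol and SAP*

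**What the plan says.** The combined protocol and SAP lists its outcomes in three places, and the lists differ.

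- **Specific aims/hypotheses** numbers two aims, each covering two outcomes. The avatar is to "decrease delirium incidence and severity" and to "decrease falls and falls with injury" more than usual care. Neither aim, and no outcome within an aim, is ranked above another.
- **Study design** says the trial will "compare outcomes on delirium, falls, sitter utilization (1:1's) and restraints between the two study groups". This brings in sitters and restraints. It does not mention severity or injurious falls.
- **The opening summary** introduces the comparison with "Based on patient medical records of sedation, restraints and incidence of falls and delirium". This is the only place where sedation appears as study data.

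The Statistical analyses section then gives one rule for everything: "Statistical significance will be defined as" p ≤ 0.05. The only test it names is this: "Pre-and post-assessment scores will be compared using paired t-tests to compare means at baseline and at hospital discharge within each group, and between groups". It names no test for falls, sitters, restraints or sedation, and does not say whether tests are one- or two-sided.

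The text contains no primary endpoint, testing order, division of alpha or multiplicity method. Both the summary and the Background look ahead to wider use if the avatar proves beneficial. Neither says which outcome, or how many, must show the benefit.

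**The concern.** A 5% threshold controls error at 5% for one test. Here the overall conclusion, that the avatar works, could be drawn from several outcomes of equal standing, so the 5% does not carry over to it. Because the lists differ and no success criterion is given, the headline outcome could also be chosen after the data are seen.

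This trial has a further reason to settle the matter. The Study design section says that randomisation mainly serves the delirium data, and that falls are grouped by unit without randomisation. With no primary endpoint, a non-randomised falls result could carry the claim of a trial presented as randomised.

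**Working it through.** **Inputs from the document.** The per-test threshold is 0.05 (Statistical analyses). The number of outcomes k is:

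- 4 from the aims alone;
- 6 with sitter use and restraints (Study design);
- 7 if sedation is counted, which is a reading, since the summary names it only as a record item.

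**Assumptions, not in the document.** Tests are two-sided, each has a true 5% error, and the avatar affects no outcome. The pairwise correlations below are illustrative.

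**The plan's own figure.** For one test, 1 − 0.95 = 5%. The plan gives no error rate for the set of outcomes. The expected enrolment of 3,650 does not enter this calculation.

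**Independent tests.** The chance of at least one p ≤ 0.05 is 1 − 0.95^k:

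- k = 4: 1 − 0.95^4 = 18.5%
- k = 6: 1 − 0.95^6 = 26.5%
- k = 7: 1 − 0.95^7 = 30.2%

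**Independent tests, favourable direction only.** The chance is 1 − 0.975^k. For k = 4 it is 9.6% and for k = 7 it is 16.2%, against 2.5% for a single two-sided test.

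**Correlated tests.** These come from a simulation of equally correlated normal test statistics (400,000 draws). At zero correlation it gives 18.5% and 30.1%, which agrees with the formula.

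| Correlation | 4 tests, either direction | 7 tests, either direction | 4 tests, favourable only | 7 tests, favourable only |
|---|---|---|---|---|
| 0.3 | 17.5% | 27.1% | 8.8% | 13.7% |
| 0.5 | 15.5% | 23.1% | 7.8% | 11.5% |
| 0.7 | 13.1% | 17.9% | 6.6% | 9.0% |

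**The count could be higher.** SPMSQ scores and the separate within-group paired tests would add comparisons. Ten independent tests would give 1 − 0.95^10 = 40.1%.

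**After the fix.** With one primary test at 0.05, and severity tested only if the primary is significant, no confirmatory claim is possible unless the primary succeeds. With no effect on either outcome, the chance of any false confirmatory claim is therefore 5%.

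**The case against.** The strongest case against is that these figures can be made to say more than they do. Three stronger readings are tempting, and the document supports none of them.

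- **That a positive claim has a 15–30% chance of being false.** This inverts the probability. The calculation starts from no effect on any outcome. The chance that a positive result is false also depends on the share of tested effects that are real, π, and on power. For one outcome it is 0.05(1 − π) / [0.05(1 − π) + power × π]. The document gives neither input. With assumed values the result runs from about 2% (π = 0.75, power 80–90%) to 47% (π = 0.10, power 50%). At π = 0.50 and power 80% it is 0.025 / (0.025 + 0.40) = 5.9%.
- **That the plan declares success if any one of seven tests is significant.** It does not. It sets a general threshold and leaves the success criterion unstated.
- **That there are seven specified tests, or four aims.** There are two aims. Tests are specified only for pre- and post-assessment scores. Sedation is not clearly an endpoint, so six is the firmer count.

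It is also fair to object that a true 5% error per test is doubtful here. Falls are compared by unit without randomisation. Patients placed on 1:1 are unenrolled, which affects the sitter outcome. The Memorial Delirium Assessment Scale is given only if the CAM is positive. Injurious falls are a subset of falls, so correlation between those two may be high. Confounding and selection may matter more than multiplicity for these outcomes, and formal alpha control would not make a non-randomised falls comparison valid.

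All of this limits the figures and shapes the remedy. It does not supply a primary endpoint. The four outcomes in the aims are enough to raise the issue even if sitters, restraints and sedation are set aside.

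**Conclusion.** The concern holds in this form: several outcomes of equal standing share one unadjusted threshold, no endpoint is primary, and the outcome lists disagree. With no true effect, the chance of at least one significant result is about 19% (four tests), 27% (six) or 30% (seven) if the tests are independent. It is lower if they are correlated, down to about 13–18% at 0.7. For results in the avatar's favour the range is roughly 8–16%, from four tests at correlation 0.5 to seven independent tests. At 0.7 it is 6.6–9.0%.

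These are approximate family-wise errors. They rest on the assumed correlations, on two-sided testing and on valid 5% component tests. The absence of a primary endpoint is judged on the text available; the data and safety monitoring plan is referred to but not included.

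**What to change.** 1. Name delirium incidence by Short CAM, compared between the randomised groups, as the single primary endpoint, tested once at two-sided 0.05. It is the first-listed outcome, it belongs to the data that randomisation is said to serve, and the Short CAM is already done at entry, on daily rounds and at the end. State the between-group test, since the plan names none for incidence.
2. Test delirium severity only if the primary is significant. State that the Memorial Delirium Assessment Scale is given only to CAM-positive patients, so this comparison covers a selected group.
3. Report falls and injurious falls (unit-level, non-randomised), sitter use, restraints and sedation with confidence intervals, as supportive or exploratory and outside the confirmatory claim.
4. Use this one list in the summary, aims, Study design and Statistical analyses sections, and fix it before outcomes are compared by group.

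The cost is wording in the protocol and SAP, with no added patients, visits or data. The downside is a stricter standard for the non-primary outcomes: a falls result alone could no longer support the main claim. Choosing delirium incidence is a recommendation; the document does not itself make that choice.
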